1.0 Study Synopsis

Study Title	Non-Significant Risk Study of a Cochlear Implant Headpiece	
Sponsor	  	
Device	
The device being evaluated is a cochlear implant headpiece and compatible selection of magnets of varying strength that allow for head-worn retention to be individualized.
	
Study Design	
Single-group, prospective, within-subjects, repeated measures, subjective report
	
Number of Participants	
Between 20 and 200 participants
	
Number of Sites	
The principal and sub-investigators at Advanced Bionics will oversee study progress. Participants will be consented and engaged at private locations across the United States and Canada by Study Staff.
	
	Inclusion Criteria	
The following criteria will be used:
 
 • Pre- or post-lingually deafened. • Fluent in English, French, Spanish or capable of communication with a caregiver who is providing consent. • Adult or child implanted with a commercially available Advanced Bionics cochlear implant. Children and adult participants are included to ensure device retention is appropriate for all implant populations. • Have (or caregivers have) the cognitive and functional capability to comply with all directions during the study • Be able to remove their own headpiece • Have (or caregivers have) the cognitive and functional capability to complete the questionnaire required for the study • Capable (or caregivers are capable) of reading and understanding patient information materials and giving written informed consent
	Exclusion Criteria	
Medical or cognitive conditions that, in the opinion of the investigators and study staff, is likely to interfere with study procedures or likely to confound evaluation of study endpoints.

	Study Objective	
The objective of this study is the evaluation of an investigational cochlear implant headpiece for individuals who are current users of FDA approved Advanced Bionics cochlear implants. This investigational headpiece and

Non-Significant Risk Study of a Cochlear Implant Headpiece

	compatible magnet is expected to provide acceptable comfort and retention for existing cochlear implant users. In this study, participants will subjectively report on their experience with the investigational headpiece during daily life.
Efficacy Parameters	Questionnaires: Self report of headpiece retention and comfort
Primary Study Endpoint	Completion of all provided questionnaires that capture subjectively reported headpiece retention and comfort, as compared to baseline.
Primary Safety Endpoint	Cumulative frequency of adverse events and events per participant
Safety Parameters	Rate of adverse events
Control	Each participant will act as their own control
Research Hypothesis	The investigational headpiece and compatible magnets will provide participants with a retention option that is acceptable for daily use.
Study Schedule	Consent: Participants or will sign an informed consent form prior to the conduct of any study procedures. Baseline: Participants will complete a questionnaire regarding experience with their own headpiece at the time of consenting and enrollment. Follow up: Participants will evaluate the investigational headpiece during a chronic period of up to one-year or until the investigational headpiece receives FDA approval. They will complete questionnaires at two-month intervals. Off-Study: Participants will return their investigational headpieces to the Sponsor.
Experimental Hypothesis	A significant portion of study participants will report that the investigational headpiece is acceptable for wear during daily life.

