3.0 Design of the clinical investigation

3.1 Study Objective

- The objective of this study is to evaluate an investigational cochlear implant headpiece for individuals who are current users of FDA approved Advanced Bionics cochlear implants. This investigational headpiece and the compatible magnet is expected to provide acceptable comfort and retention for existing cochlear implant users. In this study, participants will subjectively report on their experience with the investigational headpiece during daily life.

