- The present study is expected to continue at least for one year from initiation or until the investigational headpiece receives FDA approval, whichever comes last.

Expected duration of participation

- Duration of participation will vary from the time of enrollment to the one-year end point or until the investigational headpiece receives FDA approval, whichever comes last.

Number of participants required to be included in the clinical investigation

- A minimum of 20 participants will be enrolled in this present study, with a maximum of 200 participants.

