Following selection of the headpiece magnet and appropriate fit of the investigational headpiece, the study staff will introduce the Investigational Headpiece questionnaires that participants will complete at the initial visit and two-month intervals throughout their participation in the study. Participants will receive a number of questionnaires that would span the study duration. Pre-paid envelopes will be provided to allow participants to return completed questionnaires every two-months for the duration of the study.

At any time during the study, participants may request meetings with Investigators or Study Staff for changes in magnet strength or adjustments to the investigational headpiece, these meetings will be coordinated through a telephone call, email, or in-person conversation to set up additional visits.

Participants will return the investigational headpiece to the Sponsor at the end of this study. A pre-paid shipping envelope will be provided for this purpose.

Data collection and analysis of the present study will be administered from the Sponsor's location. Recruitment, participant consenting, and fitting of the investigational cochlear implant headpiece may be completed by study staff, with professional training with the Advanced Bionics cochlear implant system, at locations outside of the Sponsor's location. Investigators and study staff will complete training for this study that includes:

- Good Clinical Practice, including investigator responsibilities
- Informed consent procedures, including requirements for inclusion, exclusion, and all foreseeable risks
- Study protocol and procedures
- Processes for recording and reporting adverse events
- Device accountability procedures
- Data collection and correction procedures, source documentation, and record retention requirements

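### The primary study endpoint is worded as questionnaire completion, which cannot test whether the headpiece is acceptable

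*Protocol*

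**What the plan says.** The synopsis (section 1.0) has two primary endpoint rows. One is a safety endpoint based on adverse events and is not at issue. The other, the only primary endpoint on efficacy, reads "Completion of all provided questionnaires that capture subjectively reported headpiece retention and comfort, as compared to baseline".

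The protocol's aims are stated in other terms:

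- The research hypothesis is that the device offers "a retention option that is acceptable for daily use".
- The experimental hypothesis is that "A significant portion of study participants will report that the investigational headpiece is acceptable for wear during daily life".
- The objective (section 3.1) is a headpiece that "is expected to provide acceptable comfort and retention for existing cochlear implant users".
- The efficacy parameters row lists "Questionnaires: Self report of headpiece retention and comfort".

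Section 11.0 (Appendix 2) shows the data. Retention and comfort are each rated on a five-level scale from Very Acceptable to Very Unacceptable, for the personal headpiece at baseline and for the investigational headpiece afterwards.

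Section 3.4 sets the timing of the investigational-headpiece forms, "that participants will complete at the initial visit and two-month intervals throughout their participation in the study". The length of that participation is described in two ways. The synopsis says participants evaluate the headpiece "during a chronic period of up to one-year or until the investigational headpiece receives FDA approval". Section 3.3 says participation runs to the "one-year end point or until the investigational headpiece receives FDA approval, whichever comes last".

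**The concern.** The endpoint row names the ratings only to describe what the forms contain. The quantity it makes primary is their completion, which measures compliance and is also paid for, form by form (section 3.6). A primary result on completion says nothing about whether participants find the headpiece acceptable, which is what both hypotheses and the objective are about.

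A second weakness follows from tying the endpoint to every form provided. The number of forms that makes a participant complete depends on when the device is approved and on which duration statement is followed. Neither has anything to do with the headpiece's performance.

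**Working it through.** The protocol gives no power, alpha or target proportion, so there is no figure of its own to reproduce. The check is mainly of wording, with some arithmetic for scale.

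**1. What each statement measures**

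| Place | Quantity |
|---|---|
| Synopsis, primary study endpoint | Whether all forms were completed |
| Synopsis, efficacy parameters | The self-reported ratings |
| Synopsis, research hypothesis | Acceptability of retention in daily use |
| Synopsis, experimental hypothesis | Share of participants reporting the headpiece acceptable |
| Section 3.1, objective | Acceptable comfort and retention |

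Only the endpoint row is about completion.

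**2. Logical test of the endpoint**

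- A participant who returns every form marked Very Unacceptable meets the endpoint.
- A participant who answers Very Acceptable throughout but misses one form does not.

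The answers do not enter the variable, so 100% completion is compatible with any acceptability from 0% to 100%.

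**3. How many forms make a full set**

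Investigational-headpiece forms = 1 (initial visit) + floor(months of participation / 2), from section 3.4. Hence 6 months gives 1 + 3 = 4, 12 months gives 1 + 6 = 7, and 18 months gives 1 + 9 = 10. The approval months below are assumed and counted from the participant's enrolment, and the participant is assumed to have a full year available. The synopsis is read as stopping at approval or at one year, whichever is earlier.

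| Approval at | Synopsis | Section 3.3 (later of the two) |
|---|---|---|
| Month 6 | 4 | 7 |
| Month 18 | 7 | 10 |

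**4. Effect of form count on completion**

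The initial form is completed at the visit, which leaves k = 3, 6 or 9 mailed forms. If each is returned independently with probability r (both assumed), the share completing all of them is r^k.

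| r | k = 3 | k = 6 | k = 9 |
|---|---|---|---|
| 0.90 | 0.729 | 0.531 | 0.387 |
| 0.95 | 0.857 | 0.735 | 0.630 |

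With identical behaviour per form, the endpoint falls from 73% to 39% (r = 0.90) purely because the set is longer.

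**5. What the ratings could deliver**

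Taking an observed 80% acceptable (assumed), the exact (Clopper-Pearson) 95% intervals at the minimum and maximum enrolment in section 3.3 are:

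- 16/20: 56% to 94%
- 160/200: 74% to 85%

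These show only that the existing ratings support an interpretable estimate. They are not an argument for a larger sample.

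**The case against.** The strongest reply is that the intent is plain. Completion has no meaningful baseline, so the phrase comparing with baseline makes sense only for the ratings. The efficacy parameters row, the own-control row and the matching questionnaire items point the same way. Section 3.4 treats filling in forms as the means of gathering opinions. On this view the row is loosely worded, the needed data exist, and the category cut, time point and form of comparison are details for the SAP.

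The point about intent stands: a rating measure was probably meant. It does not rescue the endpoint. Even with the baseline phrase attached to the ratings, the sentence names no measure on them, and a change from baseline would not by itself match an experimental hypothesis about the share who report acceptability. Nor has the protocol simply left the matter to the SAP. It states a primary variable, and an SAP that made acceptability primary would depart from it.

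On duration, the synopsis does not say explicitly that the earlier date governs, and the one-year point in section 3.3 could be read at study level, which would give late enrollees fewer forms. The set of forms handed over under section 3.4 could also define what was provided, but its number is not given and it is tied to the study's duration. The counts in the working therefore depend on a stated reading. An upper limit of one year still conflicts with a duration set by the later of two dates.

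**Conclusion.** The concern holds. The only primary efficacy endpoint is stated on a compliance quantity and, followed literally, cannot answer either hypothesis. That conclusion rests on the wording alone and needs no numerical assumption.

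The duration conflict is a secondary defect. In the two approval scenarios considered, it shifts a full set by three forms. Those counts, and the completion rates derived from them, depend on the assumed approval months, the earliest-stop reading of the synopsis, a full year of availability, and independent returns at 90% or 95%.

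The endpoint must be corrected. The data needed for a proper one are already being collected, so the fault lies in the definition and not in the design of data collection.

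**What to change.** Restate the primary study endpoint on the ratings:

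- **Measure:** the proportion of fitted participants who rate retention, and separately comfort, Acceptable or Very Acceptable, each with an exact 95% confidence interval.
- **Time point:** one named two-month questionnaire that every participant is due to receive. The initial-visit form does not suit, because it is introduced at fitting and the hypotheses concern daily use. The month-2 form is the two-month form least exposed to the duration conflict. A later form would reflect longer wear but depends on reconciling the durations first.
- **Baseline:** report alongside it the within-participant comparison with the rating of the personal headpiece.
- **Completion:** report as a data-quality measure.

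Reconcile the duration statements in the synopsis and section 3.3.

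The SAP can hold the reference proportion, whether both ratings must meet it, the handling of No Opinion answers and missing forms, sensitivity analyses and power, provided these are fixed before the forms are analysed. No item asks about overall acceptability for wear, so the two proportions address the experimental hypothesis through its retention and comfort components.

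The cost is protocol wording: the endpoint row and the duration sentences. No new items, forms, visits or participants are needed, and no larger minimum sample is asked for. Section 5.4 requires a formal amendment with IRB approval. If reconciling the durations changes the participation schedule, section 5.3 also calls for a revised consent form and re-consent of affected participants.

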- Participants may withdraw from the study at any time, with or without reason, and without affecting continued standard of medical care they would receive.
Participants can be discontinued from the study for the following reasons:
 - Withdrawal of consent
 - A safety concern noted by a clinician that endangers the participant or cannot be tolerated for medical and/or ethical reasons
 - Inability of the participant to perform the tasks necessary to provide usable data for the study.
- The Investigator or Study Staff will complete a log to document the disposition of each enrolled participant (completed study, withdrew, discontinued). Any withdrawal or discontinued participation will be documented.

Consent

- Participants should appear to meet all of the eligibility criteria and none of the criteria for ineligibility before they are asked to consent to continue with study-specific screening procedures. Written informed consent must be obtained for all people who are potential study candidates before any study-specific tests or procedures are performed.
- Study candidates who meet general entry criteria will be asked to sign the Institutional Review Board (IRB) approved Informed Consent form before any study-specific tests or procedures are performed. Study personnel should explain that even if a patient agrees to participate in the study and signs an informed consent form, certain diagnostic or screening procedures might demonstrate that the patient is not eligible to continue participation. Examples of situations that may lead to

Non-Significant Risk Study of a Cochlear Implant Headpiece

exclusion from further participation are the presence of exclusionary medical or psychological conditions or a condition that might confound study results.

- Investigators or the Study Staff and the candidate for consent will share English, Spanish, or French language fluency.
- For study activities conducted in the State of California, research subjects will also be provided with the California Experimental Subject's Bill of Rights.

Point of enrollment

- An individual is considered to be enrolled as a study participant only after completion of the informed consent. Each participant will be provided ample time to consider participation in the trial. Once enrolled, the participant will be assigned a unique identifier. [REDACTED]

[REDACTED]

Total expected duration of the clinical investigation

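### No retention or comfort rating is scheduled when a participant leaves early, so the final view of the headpiece from those who stop is not collected

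*Protocol*

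**What the plan says.** Section 3.4 describes the investigational-headpiece questionnaires as ones that "participants will complete at the initial visit and two-month intervals throughout their participation in the study". The schedule is thus tied to continued participation.

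For the end of participation the protocol provides three things:

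- **Hardware.** The Study Schedule in the synopsis reads "Off-Study: Participants will return their investigational headpieces to the Sponsor", and Section 3.4 repeats it: "Participants will return the investigational headpiece to the Sponsor at the end of this study". A prepaid shipping envelope is supplied for this.
- **A log.** Under Section 3.3 the investigator or staff "will complete a log to document the disposition of each enrolled participant (completed study, withdrew, discontinued".
- **A record of the event.** Section 3.3 adds: "Any withdrawal or discontinued participation will be documented". It does not say whether the reason is recorded.

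Leaving is unrestricted: "Participants may withdraw from the study at any time, with or without reason". Appendix 2 holds a baseline questionnaire, a fitting form and one repeated questionnaire on retention and comfort. It has no exit form, and no section asks for the repeated form at withdrawal or discontinuation.

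**The concern.** The synopsis hypothesis is about acceptability in daily life. The rating at the initial visit is made once staff have chosen the magnet and before any daily wear, so it cannot answer that question. The two-month forms can, but only for people still taking part when a form falls due.

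Comfort and retention are the two items rated, and Section 4.2 lists discomfort and frequent falling off among the device risks. It is therefore plausible that some people who leave do so because of what the questionnaire measures. Take someone who finds the headpiece uncomfortable and leaves at week 5: the only investigational rating on file is the one from the fitting.

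At stake is the acceptable share at follow-up. If dissatisfied users leave and only returned forms are summarised, the later time points describe mainly those content to stay. An analysis plan can choose how to count the leavers, but it cannot collect a rating that was never requested.

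**Working it through.** The protocol states no dropout rate, acceptance threshold, alpha or power, so there is no planned figure to reproduce. The check has two parts.

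**1. What is on file at different exit times** (Section 3.4 schedule: initial visit, then months 2, 4, 6 and so on)

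| Exit | Investigational ratings held | Period of wear with no rating |
|---|---|---|
| Week 5 | Fitting only | All of it |
| Month 7 | Fitting, months 2, 4 and 6 | Since month 6 |

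The loss is complete for daily-life wear before month 2 and partial afterwards.

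**2. Possible size.** All inputs are assumptions:

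- s = 0.90, the share of those who stay who rate the headpiece acceptable;
- w = the share who leave with no exit rating;
- f = the share of leavers who would not rate it acceptable.

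Share acceptable among all participants: P = s(1 − w) + (1 − f)w.

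Overstatement if only those who stay are counted: s − P = w(f − (1 − s)) = w(f − 0.10).

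| w | f | P | Overstatement |
|---|---|---|---|
| 5% | 1 | 0.90 × 0.95 = 85.5% | 4.5 points |
| 15% | 1 | 0.90 × 0.85 = 76.5% | 13.5 points |
| 5% | 0.5 | 0.855 + 0.025 = 88.0% | 2.0 points |
| 15% | 0.5 | 0.765 + 0.075 = 84.0% | 6.0 points |
| 5% or 15% | 0.10 | 90.0% | 0 |

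The sign depends on f. The bias is upward only if leavers are dissatisfied more often than those who stay, and it is zero if leaving is unrelated to the rating.

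In whole people at the minimum enrolment of 20, suppose 16 of 20 would rate the headpiece acceptable (80%). If one of the four dissatisfied leaves, the forms show 16/19 = 84.2%; if two leave, 16/18 = 88.9%; if all four leave, 16/16 = 100%. If two leave and only one is dissatisfied, the forms show 15/18 = 83.3%.

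**What an analysis could do without an exit form.** Counting every leaver as not acceptable, then every leaver as acceptable, gives bounds of width w. With s = 0.90 these are 85.5% to 90.5% at w = 5% (0.855 + 0.05), and 76.5% to 91.5% at w = 15% (0.765 + 0.15). Exit ratings would narrow that interval for each leaver who returns a form.

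**The case against.** The case on the other side is substantial, and most of it limits how far the point can be taken.

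- **A reader might infer that leavers vanish from the ratings.** They do not. Every fitted participant has the initial-visit rating and any two-month ratings made before leaving.
- **A reader might infer that the result must favour the device.** The protocol does not say that leavers are dropped from the denominator. The primary endpoint is completion of the full set of questionnaires, which an early leaver fails, and the hypothesis speaks of study participants, which could mean everyone enrolled. How leavers are counted may be settled in an analysis plan that was not available here. The upward direction is therefore conditional.
- **A reader might infer that nothing can be done afterwards.** The disposition log gives a count of leavers, and a worst-case analysis needs little more. What cannot be recovered is the rating itself.
- **Departures for discomfort need not be invisible.** Sections 7.0 and 7.1 collect adverse events with severity, outcome and relationship to study materials. These are safety reports, however, and not ratings of retention or comfort.
- **Stopping wear is not leaving the study.** Section 4.2 and the questionnaire tell participants to stop wearing the headpiece if it is uncomfortable. Neither says that this ends participation. Such a person may ask for an adjustment, already holds forms and envelopes, and is paid for each form received. The protocol permits a rating by this route, but nothing triggers one.
- **One discontinuation reason does not bear on this.** "Inability of the participant to perform the tasks necessary to provide usable data for the study" concerns ability to do the study tasks, not dissatisfaction, and is no evidence of outcome-related leaving.
- **The Off-Study line is not a withdrawal rule.** It describes hardware return and is not wrong in itself. The point rests on the absence of a rating anywhere at early exit.

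What stands is the gap in data collection: no section schedules a retention or comfort rating when participation ends early.

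**Conclusion.** The point holds as a gap worth closing, not as an error or contradiction in the protocol. No rating is scheduled at early withdrawal or discontinuation. Participants who leave before month 2 have no rating after daily wear; those who leave later have none since their last form.

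An upward bias in the acceptable share follows only under two assumptions: that leaving is related to poor comfort or retention, and that the analysis uses the forms available. Its size cannot be stated from the protocol. With 90% acceptable among those who stay, the illustrated overstatement runs from zero (leaving unrelated to the rating) to 4.5 points (5% leave) or 13.5 points (15% leave, three people out of 20) if every leaver is dissatisfied. These upper figures also treat leavers as having no earlier rating that counts. The instruction to stop wear for discomfort is not questioned here.

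**What to change.** In Section 3.3 and in the synopsis Study Schedule, add that any participant who ends participation early is asked, but not required, to complete one final Investigational Headpiece Questionnaire. It should refer to the headpiece as last worn and carry the date of the last day of wear. Enclose it in the prepaid envelope already supplied for returning the device. Add to the disposition log a field for the reason for leaving, completed where the participant is willing to give it. The right to withdraw without a reason is unchanged.

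The cost is one more copy of an existing two-item form, one per-form payment and one log field. The downside is one more request to someone who is leaving. Some will not return it, so the gap will shrink but may not close.
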